## 1. Background and Significance

Bipolar disorder (BD) is characterized by debilitating depressive and manic or hypomanic episodes, effecting an estimated 45 million worldwide. The lifetime prevalence rate is estimated at 1% for BD in general, with specific prevalence rates of 0.6% for BD type-I, 0.4% for BD type-II, and 1.4% for subthreshold BD. BD is among the most impairing psychiatric disorders, typically causing pronounced deterioration in quality of life. Furthermore, BD is associated with premature mortality due to a suicide rate 10-30 times higher than the general population. The economic burden of BD on society is high, ranking 12th in causing disability worldwide according to the World Health Organization. People with BD are at particular risk of acting impulsively when experiencing manic symptoms, with a significant association between impulsivity and severity of manic symptoms. However, even when in a euthymic state, people with BD retain high impulsivity. These high-risk, impulsive, unrestrained behaviors can lead to harmful psychological, social, and financial outcomes.

FDA-approved medications for manic symptoms, such as Lithium, Carbamazepine, Valproate, and antipsychotics, have significant drawbacks due to poor tolerability, including the risk of metabolic syndrome, cognitive dulling, sexual dysfunction, and anhedonia. Consequently, nonadherence to medications is common in BD, with a reported rate of approximately 50%. This nonadherence carries a high risk of relapse, recurrence of depression, mania and psychosis, hospitalization, and suicide attempt, especially after abrupt discontinuation of medications. Overall, nonadherence decreases the likelihood of achieving remission and recovery. While medications have been shown to reduce impulsivity, with combination antipsychotics and mood stabilizers having a greater effect than mood stabilizers alone, on the whole these impulsivity scores continue to be higher than healthy controls.

There is promise in the use of device-based interventions to control manic symptoms. Prior to the advent of mood stabilizers and antipsychotic medications, electroconvulsive therapy (ECT) was the only –and very effective– intervention for mania, mixed states, and delirious mania. Nowadays, the use of ECT for the treatment of manic symptoms is limited by poor tolerability, stigma, access, lack of specialists, cost, healthcare inequity, and national laws. ***Modern noninvasive brain stimulation (NIBs) could potentially achieve the same efficacy of ECT in controlling manic symptoms, however with better tolerability, lower stigma, and easier access.***

Impulsivity, associated with poor decision-making, is a prominent manic symptom, often associated with severe functional impairment. Furthermore, as impulsivity remains high in BD subjects outside of a manic state, it may represent a core feature or trait of BD. Recent imaging studies have shown hyperactivation of ventral striatum and ventromedial PFC when anticipating rewarding outcomes in euthymic patients as well as striatal activity during anticipation being more strongly modulated by the reward value of prospects in subjects with subsyndromal hypomania. Accordingly, most treatment studies show reduced impulsivity by neuromodulation of the prefrontal cortex (PFC). Specifically, high-frequency rTMS (excitation) on right dorsolateral PFC (dlPFC) decreases hasty, impulsive choices driven by immediate reward. Therefore, it is evident that the dlPFC plays an essential role in some of the cognitive processes of impulsivity. Use of NIBs on dlPFC could reduce impulsivity in patients with bipolar disorder, depression, high

suicidality, and addictions. Similarly, bilateral, right anodal (excitation) and left cathodal tDCS on dlPFC reduces impulsivity. Therefore, excitation of right dlPFC (R-dlPFC) by NIBs is a potential mechanism for treatment of manic symptoms such as impulsivity, while preserving physical health, individual functioning, and quality of life.

Mainstream NIBs devices, such as rTMS and tDCS, are limited by the complexity of their administration, which necessitates frequent in-office sessions with specialized staff. ***Mainstream NIBs are therefore not scalable to the large needs of our society. Instead, at-home, self-administered NIBs could lead to broad access to non-stigmatizing, well-tolerated interventions for manic symptoms.*** Transcranial photobiomodulation (t-PBM) with near-infrared light (NIR) over the forehead is a novel NIBs, which is inexpensive, user-friendly and can be safely administered at home without supervision.

A substantial body of literature proves that t-PBM with NIR penetrates deeply into the cerebral cortex, modulates cortical excitability, and improves cerebral perfusion and oxygenation. Its safety was demonstrated in 1,410 acute stroke patients. t-PBM improves inhibition, attention, memory, working memory and learning, with evidence for cognitive benefits in both healthy individuals and in neuropsychiatric patients. ***t-PBM is ideally suited to excite R-dlPFC and to improve inhibition – similarly to rTMS and tDCS – with the substantial advantage that t-PBM is also suitable for in-home, self-administration.*** In the proposed study, we will test t-PBM on R-dlPFC to control impulsivity (improve decision making) in patients with a diagnosis of bipolar disorder and currently in the spectrum from euthymic to hypomanic. We will also use cerebral blood flow as the most reliable biomarker of target engagement of R-dlPFC.

Mechanistically, t-PBM with NIR (wavelength 800–1100 nm) is absorbed by the cytochrome C oxidase (CCO) in neuronal mitochondria, leading to an increased synthesis of adenosine triphosphate (ATP), along with photodissociation of nitric oxide (NO) and cerebral vasodilation and subsequent increase in cerebral blood flow (CBF). t-PBM increases cerebral blood flow (CBF) based on SPECT, Doppler Ultrasound, and fNIRS reports. This proposal will use the fMRI BOLD signal as the biomarker of CBF change induced by t-PBM. The BOLD signal was previously validated as a marker of target engagement and as a predictor of treatment outcome in other NIBs. t-PBM to the R-dlPFC led to both increase of BOLD signal and to cognitive improvement in adults with cognitive deficits. ***By engaging the CBF (BOLD), we will test the propensity of t-PBM to modulate R-dlPFC in patients with impulsivity due to bipolar disorder.***

At MGH, we are conducting a single-blind, sham-controlled (paired sample) study to test the effect of bilateral t-PBM on fMRI BOLD signal (dlPFC) in adults (n=15) with major depressive disorder. We have demonstrated feasibility for multiple t-PBM sessions per week and for the delivery of t-PBM within MRI scanner, while recording BOLD signal (NCT04366258). A collaboration between MGH and colleagues in Italy piloted bilateral t-PBM in adults (n=4) with BD. t-PBM was helpful in alleviating BD residuals, including impulsivity and irritability.

## 2. Specific Aims and Objectives

**1. To test the effect of a single t-PBM session on cerebral blood flow (CBF), while irradiating R-dlPFC, in subjects with impulsivity due to BD**

*Hypothesis:* a single t-PBM session on the R-dlPFC will significantly increase BOLD-signal at the R-dlPFC, relative to sham.

**2. To test the effect of repeated t-PBM sessions on CBF, after irradiating R-dlPFC, in subjects with impulsivity due to BD**

*Hypothesis:* repeated t-PBM sessions on the R-dlPFC will significantly increase BOLD-signal at the R-dlPFC at day 5 relative to baseline.

**3. To test the effect of repeated t-PBM sessions on impaired decision making, in subjects with impulsivity due to BD**

*Hypothesis:* repeated t-PBM sessions on the R-dlPFC will significantly improve decision making – increase in net gain at the Iowa gambling task, decrease in Barratt Impulsiveness Scale (BIS) score at day 5 and follow-up visit relative to baseline, decrease in BRIEF-A score at day 5 and follow-up visit relative to baseline, and a decrease in I-7 Impulsiveness and Venturesomeness Questionnaire score at day 5 and follow-up visit relative to baseline.

**4. To test the effect of repeated t-PBM sessions on manic symptoms (MOODS-SR) in subjects with BD**

*Hypothesis:* repeated t-PBM sessions on the R-dlPFC will significantly decrease the total Mood Spectrum-Self Report (MOODS-SR) score at day 5 and follow-up visit relative to baseline. Dimensional improvements will be analyzed as a secondary step.

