### **3. General Description of Study Design**

This is a single-blind study to test the neuropsychological and clinical effects of t-PBM with NIR in BD. For our primary aim of examining the effect of tPBM on CBF, the study is additionally sham-controlled. Twenty patients with a diagnosis of bipolar disorder, not currently in a depressive, manic, or mixed state episode, will undergo one sham and one NIR- t-PBM session on day 1 (within MRI scanner), and one daily NIR- t-PBM session from day 2 to 5. On day 5, the NIR t-PBM session will also occur in the MRI scanner. The fMRI scan will measure BOLD changes during sham t-PBM (day 1) and during NIR t-PBM (day 1 & 5), on R-dlPFC.

Impulsivity will be assessed by the BIS at pre-screen (for inclusion criteria), baseline, treatment day 5, and the follow-up visit; and by the gambling tasks at baseline, after the first NIR t-PBM (day 1), after the fifth NIR t-PBM (day 5), and at the follow-up visit. Other aspects of impulsivity and executive functioning will be assessed by the I-7 and BRIEF-A at baseline, day 5, and the follow-up visit. The MOODS-SR-Last Week will be administered at baseline, day 5, and the follow-up visit to assess change in mood, particularly hypomanic symptoms. At screening, subjects will complete the MOODS-SR Lifetime.

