This 161-item self-report scale assesses manic-depressive symptoms. Participants are asked to answer “Yes” or “No” to each question. Subdomains measure Moods, Energy, Cognition, and Rhythmicity. Time frame is either lifetime or the last week, depending on scale used.

*MRI Safety Checklist*

This form identifies risk factors that may make MRI participation unsafe.

*New Immigrant Survey-Skin Color Scale (NIS-SCS)*

The NIS-SCS is an 11-point scale, ranging from zero to 10, with zero representing albinism, or the total absence of color, and 10 representing the darkest possible skin. The ten shades of skin color corresponding to the points 1 to 10 on the Massey and Martin Skin Color Scale are depicted in a chart, with each point represented by a hand, of identical form, but differing in color. The respondent never sees the chart. We gather this data for use as a potential covariate in analyses as skin color can affect absorption of NIR.

*Patient Health Questionnaire (PHQ-9)*

This nine-item self-report measure assesses the presence and severity of depressive symptoms over the past 14 days. This scale will be administered as part of the pre-screening phase.

*Perceived Blinding Questionnaire (PBQ)*

The PBQ is a self-report questionnaire to determine the degree to which the participant believes they are receiving active treatment or sham.

*Prior Treatment Log*

This form captures information regarding prior treatments for bipolar disorder or other mental health concerns.

*Systematic Assessment for Treatment Emergent Events (SAFTEE)*

The SAFTEE is a commonly used instrument originally developed by NIMH and adapted into a self-report instrument. The version of the scale that we plan to use is the same used by the multi-center, NIMH-sponsored CO-MED trial, and it examines in a systematic fashion all possible treatment-emergent side effects and probes specific adverse symptoms, including suicidal thoughts and behaviors, and self-injurious behavior.

*t-PBM Self-Report Questionnaire (TSRQ)*

An open-ended questionnaire focusing on potential inconveniences and discomforts from the t-PBM treatment.

*Young Mania Rating Scale (YMRS)*

This 11-item clinician-rated scale is used to assess the presence and severity of manic symptoms.

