## 9. Statistical Analysis

Preprocessing of MRI and fMRI data will be performed with the FreeSurfer software package, scripted in Bash. Slice-time correction, motion-correction, and co-registration of functional BOLD scans, Time of Repetition (TR), and participant will then be performed. BOLD signals will then be smoothed to a full-width half maximum (FWHM) of 3mm and z-scored at every voxel.

t-PBM related increase of BOLD percent signal change (PSC) averaged across all ROI voxels will be assessed during the first scanning session where the participant receives both sham and NIR over the R-dlPFC. PSC of t-PBM related increase in BOLD both during and after stimulation will be the dependent variable with the independent variable being the condition of t-PBM during the first session (sham vs. NIR).

BOLD signal will again be assessed during the 5th NIR session as a PSC across all ROI voxels in comparison with the BOLD PSC from the first NIR session to observe any BOLD changes after 5 NIR treatment sessions. The dependent variable will be the BOLD signal and the independent variable will be the timepoint: day 1 vs. after 5 sessions (day 5).

For both gambling tasks, the gambling task net gain score will be analyzed for changes from baseline to after treatment on day 1, baseline vs day 5, and baseline vs follow up. The BIS, BRIEF-A, and I-7 will be analyzed for changes from baseline to day 5 and follow up. Here, the dependent variable will be the gambling tasks' net gain scores, BIS, BRIEF-A, and I-7 total score. The independent variable is the timepoint baseline vs. day 5 (for the gambling tasks) and follow up. The MOOD-SR will also be analyzed for a decrease in impulsivity at each timepoint of baseline vs. day 5 and follow up. A General Mixed Models Regression will be used with time as a fixed effect and subject as a random effect.

Secondary analyses will also be performed for the BIS, BRIEF-A, I-7, MOOD-SR, SAFTEE, and TSRQ. Each scale and their respective subscales will be analyzed for specific changes at

each timepoint to better understand the effect t-PBM NIR has on the symptoms and presentation of BD. These additional analyses will also be helpful in assessing the initial safety profile of t-PBM in this psychiatric population.

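### Aim 4 names manic symptoms but tests the MOODS-SR total, which is not specific to mania, and no manic component or other mania-specific change measure is pre-specified.

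*Combined protocol and SAP*

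**What the plan says.** Section 2 states Aim 4 as "To test the effect of repeated t-PBM sessions on manic symptoms (MOODS-SR) in subjects with BD". Its hypothesis is that repeated sessions "will significantly decrease the total Mood Spectrum-Self Report (MOODS-SR) score at day 5 and follow-up visit relative to baseline", followed by "Dimensional improvements will be analyzed as a secondary step".

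The Assessments part of Section 6 describes the instrument: "This 161-item self-report scale assesses manic-depressive symptoms". Items are answered yes or no, and "Subdomains measure Moods, Energy, Cognition, and Rhythmicity". No manic or depressive score is defined.

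Two other places describe what the scale is for. Section 3 says it is given "to assess change in mood, particularly hypomanic symptoms". Section 9 says "The MOOD-SR will also be analyzed for a decrease in impulsivity at each timepoint". Section 9 also plans secondary analyses of each scale and its subscales, without tying any of them to mania.

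The YMRS is described as follows: "This 11-item clinician-rated scale is used to assess the presence and severity of manic symptoms". In Section 6 it is listed at the Baseline Visit and not at Treatment 5 or the Follow Up Visit.

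**The concern.** The conclusion of Aim 4 is to be about mania, but the score tested pools both poles of the mood spectrum. Followed as written, a fall in depressive items alone would confirm a hypothesis about manic symptoms. A fall in manic items offset by a rise in depressive items would count against it.

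The Section 9 label adds to the difficulty, because impulsivity is the target of Aim 3, which has its own instruments. Someone working from Section 9 alone would not know which claim a significant MOODS-SR result supports. If a manic sub-score were put together later to settle the matter, it would be chosen after the data had been seen.

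**Working it through.** There is no Aim 4 figure to reproduce: Section 9 gives a power statement for Aim 1 only. The check is therefore mainly a comparison of passages, with an illustrative calculation after it.

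**Comparison**

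- Construct: manic symptoms (Section 2, Aim 4); mood with emphasis on hypomania (Section 3); impulsivity (Section 9). That is three labels for one outcome.
- Score tested: the total of a 161-item scale of manic-depressive symptoms (Section 2; Section 6, Assessments).
- Could the secondary analyses isolate mania? Aim 4 does not name its dimensions. The listed subdomains are moods, energy, cognition and rhythmicity, and none is identified as manic.
- Could another scale measure manic change? The YMRS has a baseline value only. The ASRM belongs to pre-screening and reappears only as an optional aid to the clinical check-in call, where it need not be completed. Neither gives a planned change score.
- Is the baseline secured? Section 3 schedules the Last Week form at baseline, but the Baseline Visit list in Section 6 omits it. The Lifetime form at screening covers a different period and cannot replace it.

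**Illustration**

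Assumptions, none of them from the documents: the total is a manic part plus an other part with equal change SDs; their changes correlate at r; the manic part improves by d_m = 0.5; alpha is 0.05; a paired t-test stands in for one baseline-to-timepoint contrast of the planned mixed model. The sample size of 20 is the protocol's.

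With d_o the effect on the other part:

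d_total = (d_m + d_o) / √(2 + 2r)

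Power is the probability that a noncentral t with 19 degrees of freedom and noncentrality d√20 exceeds the critical value. Two-sided figures count rejections in the direction of improvement.

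Testing the manic part alone gives 69.5% one-sided and 56.4% two-sided. Testing the total gives, for r = 0 / 0.3 / 0.6:

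| Other part | d_total | One-sided power, % | Two-sided power, % |
|---|---|---|---|
| no change (0) | 0.354 / 0.310 / 0.280 | 45.2 / 37.9 / 33.0 | 32.3 / 26.0 / 22.0 |
| improves by 0.25 | 0.530 / 0.465 / 0.419 | 73.9 / 64.1 / 56.5 | 61.4 / 50.6 / 42.9 |
| improves by 0.5 | 0.707 / 0.620 / 0.559 | 92.0 / 84.8 / 77.8 | 85.1 / 74.9 / 66.0 |
| worsens by 0.25 | 0.177 / 0.155 / 0.140 | 18.9 / 16.5 / 14.9 | 11.3 / 9.7 / 8.6 |
| worsens by 0.5 | 0 / 0 / 0 | 5.0 | 2.5 (5.0 over both tails) |

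For example, the first entry is 0.5/√2 = 0.354.

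The formula is symmetric in its two parts, so the first row also covers the reverse case: no manic change and an improvement of 0.5 in the other part. The total would then be significant with probability 33% to 45% one-sided, with nothing having happened to mania.

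**The case against.** The strongest reply is that the plan already looks below the total. Aim 4 promises a dimensional step and Section 9 promises subscale analyses, so a fall confined to one domain would probably be noticed. In an exploratory aim, whether the total or a dimension comes first is partly preference. This lowers the severity but does not close the gap, because no manic component is named in either place.

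A second reply is that impulsivity is not foreign to the aim, since Section 1 calls it a prominent manic symptom. That is fair. A reader might infer from Section 9 that the wrong construct is being tested; the documents support only a loose label that should match Aim 4.

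A third reply concerns the sample. A reader might infer that people outside an episode have few manic items to lose, so other items must drive the total. The documents do not support this. Section 1 places participants between euthymic and hypomanic, and Section 4 excludes current depressive, manic and mixed episodes without listing hypomania. Depressive items may be at least as sparse as manic ones. A change driven by depressive items remains possible, but nothing in the plan makes it the expected case.

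Finally, the documents provide no scoring key, so a manic score cannot be assumed to exist ready-made. This stands, and the remedy has to be conditional on one being definable.

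**Conclusion.** The mismatch holds on the protocol's own description of the scale. The total is non-specific rather than unrelated to mania, so it would go too far to say that Aim 4 does not measure manic symptoms at all. What cannot be done is to attribute a change in the total, or its absence, to mania, and no mania-specific change measure is pre-specified to settle the question.

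No single power loss should be quoted as the cost. The fall from about 56% to 32% two-sided (70% to 45% one-sided) needs an independent, equal-variance manic part and no other change. Power drops to alpha if depressive items worsen equally. It rises if both parts improve equally, but that result could not be credited to mania. The item split and the effect size are unknown.

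Nor should the omission from the Baseline Visit list be read as proof that the Last Week form will not be collected then, because Section 3 schedules it. The two sections need to be reconciled.

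The correction should be made, at low priority. Section 3 identifies cerebral blood flow as the primary aim, Aim 4 has no power statement, and its comparison over repeated sessions has no sham control. A better score would not by itself establish an effect on mania.

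**What to change.** Before any outcome data are seen:

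1. Specify which items of the MOODS-SR Last Week form make up the manic component and make that score the Aim 4 outcome. Keep the total and the depressive component as secondary outcomes.
2. If no such score can be defined, reword Aim 4 and its conclusion to overall mood-spectrum symptoms and keep the total.
3. In Section 9, replace the reference to impulsivity in the MOODS-SR sentence with the Aim 4 construct.
4. Reconcile the Baseline Visit list in Section 6 with Section 3 so that the Last Week form appears at baseline.

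The cost is scoring and wording. The questionnaire is already planned at baseline (Section 3), day 5 and follow-up, so no procedure is added. Item 1 also requires a documented scoring rule, which the protocol does not now contain.

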### **3. General Description of Study Design**

This is a single-blind study to test the neuropsychological and clinical effects of t-PBM with NIR in BD. For our primary aim of examining the effect of tPBM on CBF, the study is additionally sham-controlled. Twenty patients with a diagnosis of bipolar disorder, not currently in a depressive, manic, or mixed state episode, will undergo one sham and one NIR- t-PBM session on day 1 (within MRI scanner), and one daily NIR- t-PBM session from day 2 to 5. On day 5, the NIR t-PBM session will also occur in the MRI scanner. The fMRI scan will measure BOLD changes during sham t-PBM (day 1) and during NIR t-PBM (day 1 & 5), on R-dlPFC.

Impulsivity will be assessed by the BIS at pre-screen (for inclusion criteria), baseline, treatment day 5, and the follow-up visit; and by the gambling tasks at baseline, after the first NIR t-PBM (day 1), after the fifth NIR t-PBM (day 5), and at the follow-up visit. Other aspects of impulsivity and executive functioning will be assessed by the I-7 and BRIEF-A at baseline, day 5, and the follow-up visit. The MOODS-SR-Last Week will be administered at baseline, day 5, and the follow-up visit to assess change in mood, particularly hypomanic symptoms. At screening, subjects will complete the MOODS-SR Lifetime.

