### *Baseline Visit*

Adverse events, as well as concomitant medications and therapies, will be collected. Participants will complete the Young Mania Rating Scale (YMRS), the BIS, the BRIEF-A, the I-7, the CAST-IRR, and the SAFTEE. A licensed clinician will administer the C-SSRS and the CGI-S. Skin color will be recorded using the NIS-SCS. Participants will complete two computerized gambling tasks: The Iowa gambling task and the Delgado gambling task. The order of administration of the gambling tasks will be randomized. This appointment will last approximately 90 minutes.

*Treatment 1*

Vitals will be assessed and recorded. The MRI Safety Checklist will be completed and signed before the MRI. Participants will undergo an MRI Scan. While in the scanner, participants will first undergo a structural scan and resting state scan, followed by a functional scan during which the participants will receive a sham t-PBM treatment. This scan will be followed by a pre-stimulation resting-state functional acquisition. At this time, active t-PBM will be administered, immediately followed by a post-stimulation resting state scan. Participants will then complete the Delgado gambling task. A functional sequence will be collected during the administration of the gambling task. Finally, participants will undergo a post-stimulation resting state functional scan. The MRI will last approximately 75 minutes in total.

Participants will know that they are receiving both active and sham treatment, but they will not be told in which order the treatments will be delivered. Participants will complete the PBQ, CAST-IRR, TSRQ, and the Iowa Gambling Task at the conclusion of the visit. Study staff will complete an intervention tracking form.

*Treatments 2-4*

Treatments 2, 3, and 4 should ideally occur once daily during the three days following the first treatment administration. If necessary, this window can be extended so that these three treatment visits occur within ten days of the Baseline/Treatment 1 visit (in this case, the timing of follow up visits will be adjusted accordingly). Adverse events and concomitant medications and therapies will be assessed and recorded at each visit. Participants will complete the TSRQ and CAST-IRR after treatment administration. Study staff will complete an intervention tracking form for each study visit.

*Treatment 5*

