Treatment 5 should ideally occur the day after Treatment 4. If necessary, this window can be extended so that this visit occurs within ten days of the Treatment 1 visit (in this case, the timing of follow up visits will be adjusted accordingly). Adverse events, concomitant medications and therapies, and vitals will be assessed and recorded. The MRI Safety Checklist will be completed and signed before the MRI. Participants will complete the MOODS-SR, the BIS, the BRIEF-A, and the I-7.

Participants will undergo an MRI Scan. A structural scan and a pre-stimulation resting state functional scan will be collected first. Active t-PBM will be administered immediately after the resting-state scan, followed by a post-stimulation resting state functional scan. Participants will then complete the Delgado gambling task. A functional sequence will be collected during the gambling task administration. The MRI will last approximately 45 minutes in total.

Participants will complete the SAFTEE, the CAST-IRR, the TSRQ, and the Iowa gambling task after the MRI/t-PBM session. Study staff will complete an intervention tracking form.

*Clinical Check-in Call*

A licensed study clinician will call the participant (phone or video call) approximately 2-3 days after the final treatment session. Adverse events and concomitant medications and therapies will be assessed and recorded. The clinician will administer the C-SSRS and the CGI-S/I. The clinician may use the PHQ-9 and/or ASRM to guide their call with the study participant, though these scales do not need to be completed in full. The purpose of this call is to check in on the general safety and well-being of the participant.

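### The single-blind label in Section 3 is attached to the clinical and neuropsychological effects, but the only blind described is the day-1 order of sham and NIR, so no Aim 3 or Aim 4 contrast is blinded or controlled

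*Combined protocol and SAP*

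**What the plan says.** Section 3 opens with "This is a single-blind study to test the neuropsychological and clinical effects of t-PBM with NIR in BD" and continues: "For our primary aim of examining the effect of tPBM on CBF, the study is additionally sham-controlled". Read together, the blind is claimed for the neuropsychological and clinical effects, and the sham control is an extra feature for the blood-flow aim.

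Section 3 then gives the treatment sequence. Each participant "will undergo one sham and one NIR- t-PBM session on day 1 (within MRI scanner"), followed by "one daily NIR- t-PBM session from day 2 to 5". Section 6, Treatment 1, says participants know they will get both conditions but "they will not be told in which order the treatments will be delivered". Section 6, Treatment 5, confirms the last session is NIR: "Active t-PBM will be administered immediately after the resting-state scan".

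Aims 3 and 4 in Section 2 are worded as tests of an effect. The Aim 3 hypothesis is that "repeated t-PBM sessions on the R-dlPFC will significantly improve decision making", and the Aim 4 hypothesis is a fall in the MOODS-SR total. Both are judged against baseline. Section 9 analyses these outcomes with a mixed model that has time as a fixed effect and subject as a random effect.

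**The concern.** A single-blind label tells the reader that participants did not know which condition they were under when the outcome was produced. For Aims 3 and 4 there is only one condition to be under. BIS, BRIEF-A, I-7 and MOODS-SR are self-reports, so they are open to expectancy. The gambling tasks are repeated at baseline, Treatment 1, Treatment 5 and follow-up, so they are open to practice. Any of these can move a score from baseline without a device effect.

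At stake is what Aims 3 and 4 can conclude. With the present label and wording, a fall in impulsivity or manic symptoms could be read as a blinded finding that t-PBM caused it. The design cannot support that reading.

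**Working it through.** **1. What is concealed, and when.** The plan's own entries, side by side:

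| Stage | Sessions received | Concealment described | Aim 3-4 outcomes collected |
|---|---|---|---|
| Baseline | none | not applicable | questionnaires and both gambling tasks |
| Treatment 1 | one sham, one NIR | order of the two | Delgado task after NIR; Iowa task at end of visit |
| Treatments 2-4 | NIR | none | none |
| Treatment 5 | NIR | none | questionnaires listed before the scan; Delgado and Iowa tasks after NIR |
| Follow-up | none | none | questionnaires and both gambling tasks |

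The Perceived Blinding Questionnaire is listed at Treatment 1 and at no other visit.

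**2. Does the day-1 blind reach any Aim 3-4 outcome?** Section 6 places sham in the early functional scan ("followed by a functional scan during which the participants will receive a sham t-PBM treatment"). A resting-state acquisition and then NIR follow, and both tasks come after NIR. Nothing behavioural or clinical is measured between the two conditions. Even the baseline-to-day-1 task comparison is therefore before versus after both conditions, not sham versus NIR. The blind serves the Aim 1 BOLD comparison only.

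**3. Does the model supply a control?** No. Time is the only fixed effect, and there is no treatment term because there is no second treatment over this period. The time coefficient is the sum of any device effect, expectancy, practice, passage of time and regression to the mean. On the last of these, entry requires a BIS total of at least 70 at pre-screen. The scale is taken again at baseline, so some regression may already have occurred by then, but the design cannot measure what remains.

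**4. Number of sessions before each self-report.** At Treatment 5 the questionnaires are listed ahead of the scan in which the fifth NIR session is given. As written, the Day 5 self-reports follow four NIR sessions (Treatments 1-4) and the follow-up self-reports follow five. The sessions need not fall on consecutive days, because Section 6 allows a ten-day window.

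**5. How many contrasts are self-report.** Section 9 lists 4 scales x 2 time points = 8 self-report contrasts, and 2 tasks x 3 time points = 6 task contrasts. That gives 8 of 14. The Aim 3 hypothesis names only the Iowa task; on that reading there are 3 task contrasts and the count is 8 of 11.

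**6. Illustration of size.** The plan has no figure to reproduce here, because its power statement covers Aim 1 only. Assumptions: 20 complete pairs (Section 3 gives 20 participants), a paired t-test standing in for the mixed model, two-sided alpha 0.05, no device effect, and a non-device shift of d standard deviations of the paired difference. The values of d are assumed.

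- Critical value: t(0.975, 19 df) = 2.093.
- Noncentrality: d x sqrt(20).
- Rejection probability: P(|T| > 2.093), with T noncentral t on 19 df.

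| Assumed d | d x sqrt(20) | Probability of significance |
|---|---|---|
| 0.2 | 0.894 | 0.136 |
| 0.3 | 1.342 | 0.247 |
| 0.5 | 2.236 | 0.565 |

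With no shift the figure would be 0.05.

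**The case against.** The strongest reply is that the plan does not hide the missing control. Section 3 confines the sham to the primary aim, the power paragraph covers Aim 1 only, Section 7 says the study is not a test of t-PBM as a treatment for bipolar disorder, and Section 8 calls the effects on impulsivity unknown. The Aim 3 and 4 hypotheses are also openly stated against baseline. All of this stands and lowers the risk of misreading. It does not correct the sentence that ties the blind to the clinical and neuropsychological effects, nor the causal wording of Aims 3 and 4 and of the secondary analyses in Section 9.

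A second reply is that the rejection rates measure the chosen shifts and not the harm done by a label. That is right. Any bias of the same size would give the same rates, so they are an illustration only.

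Stronger readings are tempting but not supported:

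- **Aims 2-4 are open-label.** A reader might infer this, but nothing states what participants are told about Treatments 2-5, and the consent pages are not available. What is documented is that no blinding is described.
- **The clinician ratings contradict the label.** They do not. Single-blind makes no claim about raters, and CGI is neither an Aim 3-4 outcome nor part of the Section 9 analyses.
- **All self-reports come right after five consecutive sessions.** The listed order at Treatment 5 and the ten-day window say otherwise.
- **Aim 2 carries the same expectancy problem.** Its outcome is BOLD, which is not a self-report. It is uncontrolled and confounded with time, but the expectancy argument does not carry over to it.

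**Conclusion.** The single-blind statement in Section 3 is wrong as written for the outcomes it names. This follows from the plan's own procedures and needs no numerical assumption: the described blind covers the day-1 order only, and every Aim 3-4 contrast is an uncontrolled comparison with baseline. A significant result on those aims would show change over time, not an effect of t-PBM.

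How often a non-device shift alone would reach significance cannot be settled from the documents. The range of roughly 14% to 56% per contrast depends entirely on assumed shifts of 0.2 to 0.5 SD, complete data on 20 participants, and the paired t-test as a stand-in for the mixed model. The sham-controlled Aim 1 comparison is not touched by this point.

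**What to change.** In Section 3, replace the general single-blind statement with two statements: the described blind covers only participants' knowledge of the order of sham and NIR on day 1 (Aim 1); and Aims 2-4 are uncontrolled within-subject comparisons over time, with no blinding described.

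In Section 9, state that Aim 3-4 results will be reported as change from baseline and as hypothesis-generating, not as a blinded or causal effect of t-PBM. This agrees with the position already taken in Section 7. The effect wording of Aims 3 and 4 in Section 2 should be read, and preferably rephrased, in the same terms.

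The cost is a text amendment with no change to visits, sample size or analyses. The downside for the sponsor is a less favourable design label and narrower conclusions for Aims 3 and 4.
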